6.3 Enrollment

Patients will be randomized after completion of baseline assessment to either usual care or “nudges to quit”. Once randomization occurs, the participant will be considered enrolled.

6.4 Intervention:

Nudges to Quit-

a. Patient:

- i. Content: Patients will receive a basic handout (example attached) for patient education on evidence-based Guideline-recommended tobacco treatment and a nudge report based on patient reported treatment needs (example attached).
- ii. *Delivery methods:*
 - a. *Mailed and Email Delivery:* A patient handout and patient nudge to quit mailed and/or emailed (password protected with pin number, if emailed) to participants.
 - b. *Verbal Delivery:* A study team member will deliver the patient nudge with a brief coaching interaction based on the public health service guidelines and 5A's approach.
- iii. *Timing:* We will deliver the intervention report on the day of or <=7 days of the baseline visit. A booster intervention report will be mailed and/or emailed in 1 month following the baseline visit.

b. *Provider :*

- i. Content: Providers will receive a nudge report (example attached) based on patient reported treatment needs. For example, providers will receive a nudge message informing them of their patients' cigarettes smoked per day, interest in medication and free smoking cessation programs, and guidance on what they can do to help their patient. Attached to the message will be a triage card that encourages providers to give advice and refer. Triage cards will also correspond to patient interest profiles.
- ii. *Delivery Methods:* The providers of the participants will be sent via secure email and/or inbasket message.
- iii. *Timing:* We will deliver the intervention report on the day of or <=7 days of the baseline visit. A booster intervention report will be mailed and/or emailed in ~1 month following the baseline visit.

Usual Care:

- a. *Patient:*
 - i. Content: Patients will receive a basic handout (example attached) for patient education on evidence-based Guideline-recommended tobacco treatment.
 - ii. *Delivery Methods:*
 - a. *1. Mailed and Email Delivery:* A patient handout and patient nudge to quit will be mailed and/or emailed (password protected with pin number, if emailed) to participants.
 - b. *Verbal Delivery:* A study team member will deliver the patient nudge with a brief coaching interaction based on the public health service guidelines and 5A's approach.
 - iii. *Timing:* We will deliver the intervention report on the day of or <=7 days of 3 month visit.
- b. *Provider:* Providers will maintain their usual care without receiving any reports.

INTERVENTION	Arm 1: Nudges to Quit (NTQ)	Arm 2: UC
Patient level		
Patient Basic Handout (mail, email and verbal delivery by a research team member if applicable)	X	X

Patient Nudges to quit report (mail, email and verbal delivery by a research team member if applicable)	X	
Provider level (Patient will provide consent for us to send the report to their doctor)		
Provider Nudges to quit report (email and inbasket message, if applicable)	X	
Timing of intervention	Baseline (<=7 days within enrollment) and Booster (1 month)	Baseline (<=7 days within enrollment) and

1. Outcomes will be assessed at 3 months post-intervention.
2. After 3 months, patients in Arm 2 (UC) will receive NTQ intervention. Patients in Arm 1 will continue with their study participation with no change. This will allow the Arm 2: UC to receive the intervention at a delayed timing. This will allow additional secondary comparisons (e.g., patients assigned to the UC arm may have increased treatment as they transition from UC to NTQ intervention.)
3. At 6 months patients in both arms will receive the 6 month follow up assessment.

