6.2 Patient participation

Patients who participate will be asked to complete 3 assessments either over the phone, in person on paper or via secure redcap questionnaire administered by a research team member. Patients will be asked to complete a pre-appointment tobacco treatment needs assessment (baseline). This assessment will collect demographic, smoking, and treatment information about the patient (see trial overview table), and in part will be used as decision support for their provider via nudge creation. If patients are randomized to nudges to quit their provider will receive the nudge within one week post pre-appointment tobacco treatment needs assessment. At three month and three six months, the study team will assess tobacco treatment and smoking behaviors such as readiness to quit, smoking abstinence, smoking quantity, and quit attempts. If patients are randomized to usual care, the provider will receive the nudge following three month assessment.

These assessments will occur at study visits outside of regular clinic visits.

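### The only stated Aim 1 comparison is at month 6, after usual care is due to receive the nudge, so it contrasts immediate with delayed delivery, not Nudges to Quit with usual care

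*Combined protocol and SAP*

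**What the plan says.** All references are to the combined protocol and SAP.

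- **Aim 1 (section 9).** The hypothesis is that more patients receive cessation treatment with NTQ than with usual care. The only analysis given is a comparison of receipt across the two arms at the 6-month visit. The section adds that the pilot's estimates will feed power calculations for an R01 proposal, and that no statistical tests will be done.
- **Delayed delivery (section 6.4).** The usual-care Delivery Methods include the patient nudge and brief coaching, and the Timing line places the report within 7 days of the 3-month visit. Note 2 under the intervention table says: "After 3 months, patients in Arm 2 (UC) will receive NTQ intervention". It continues: "This will allow additional secondary comparisons", with the example that "patients assigned to the UC arm may have increased treatment as they transition from UC to NTQ intervention".
- **Outcome time (section 6.4, note 1).** "Outcomes will be assessed at 3 months post-intervention". No aim is named.
- **Provider report.** Section 6.4 makes it part of NTQ: "Providers will receive a nudge report (example attached) based on patient reported treatment needs". For usual care, section 6.2 says: "If patients are randomized to usual care, the provider will receive the nudge following three month assessment". The Provider line of the usual-care block in section 6.4 says: "Providers will maintain their usual care without receiving any reports".

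**The concern.** The Aim 1 hypothesis needs a comparison arm that is still under usual care when receipt is measured. Section 9 measures it after that arm is scheduled to be switched. Estimates for planning the next trial are a stated purpose of this pilot. If the 6-month difference is taken forward as NTQ versus usual care, the R01 power calculation would rest on a different contrast from the one named.

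A second, lesser matter is what the delayed package contains. Sections 6.2 and 6.4 differ on whether the usual-care provider ever gets a report, so even a correctly labelled 6-month comparison is not fully defined.

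**Working it through.** The plan gives no event rates, effect size, alpha or power, so there is no figure to reproduce. The check is the schedule set against the analysis, followed by an illustration on assumed rates.

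**1. Patients affected.** Section 6.1: 60 patients at 1:1, so 60 / 2 = 30 in usual care.

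**2. Time since first delivery at the 6-month visit.** Visits are taken at nominal dates with a month of 30.44 days, so month 3 = 91.3 days and month 6 = 182.6 days.

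- NTQ arm, patient and provider reports, delivered 0 to 7 days after baseline: 182.6 − (0 to 7) = 175.6 to 182.6 days, or 5.8 to 6.0 months.
- Usual-care patient nudge, delivered 0 to 7 days after the 3-month visit: 182.6 − 91.3 − (0 to 7) = 84.3 to 91.3 days, or 2.8 to 3.0 months.
- Usual-care provider report: at most 91.3 days (3.0 months) under section 6.2, which sets no day limit; never, if the section 6.4 Provider line applies after month 3.

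**3. What each visit contrasts.**

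| Visit | Provider report sent after month 3 | Provider report never sent |
|---|---|---|
| Month 3 | NTQ vs usual care | NTQ vs usual care |
| Month 6 | Immediate vs delayed NTQ | Immediate NTQ vs delayed patient-only nudge |

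Neither month-6 entry is the contrast in the hypothesis. Both month-3 entries are.

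**4. Illustration that the contrasts are not interchangeable.** All rates here are assumptions. Let u and t be the chance of receiving treatment in a 3-month period under usual care and under NTQ, with (u, t) = (10%, 30%), (20%, 40%) and (30%, 50%). The month-3 difference is then 20 points in each case. Cumulative receipt by month 6 is 1 − (1 − p1)(1 − p2), where p1 and p2 apply to the two periods. In months 3 to 6 the NTQ arm either falls back to u (no carryover) or stays at t (full carryover). A patient-only nudge is given half the effect, h = (u + t)/2.

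For u = 20%, t = 40%, h = 30%:

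- NTQ arm: 1 − 0.6 × 0.8 = 52% (no carryover) or 1 − 0.6 × 0.6 = 64% (full carryover).
- Usual care never nudged: 1 − 0.8 × 0.8 = 36%; difference 16 or 28 points.
- Delayed full NTQ: 1 − 0.8 × 0.6 = 52%; difference 0 or 12 points.
- Delayed patient-only nudge: 1 − 0.8 × 0.7 = 44%; difference 8 or 20 points.

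Over all three pairs the month-6 difference is 14 to 32 points if usual care is never nudged, 0 to 14 with delayed full NTQ, and 7 to 23 with a delayed patient-only nudge.

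**5. Period of receipt.** Section 9 does not say whether receipt counts from baseline, from month 3, or only as current at the visit. Step 4 counts from baseline. Counting months 3 to 6 only, on the same assumptions, the difference against delayed full NTQ is u − t = −20 points (no carryover) or t − t = 0 (full carryover). The undefined window alone can change the answer.

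**The case against.** The strongest reply is that the plan is a pilot with no tests, that month-3 data are collected anyway, and that section 9 does not say which estimates go into the R01. All of that is true, and it makes the harm conditional on how the 6-month figure is used. It does not remove the mismatch: the 6-month comparison is the only one stated for a hypothesis about NTQ over usual care.

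Several stronger readings are tempting, and the documents do not support them.

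- *Note 1 and section 9 contradict each other on the Aim 1 time point.* Note 1 names no aim and does not exclude month 6, and both assessments are scheduled. It points toward month 3, as does note 2's description of the later comparisons as secondary, but this is tension and not strict contradiction.
- *The provider conflict undermines Aim 1.* It does not change the main conclusion: month 6 is not NTQ versus usual care whether or not the report is sent, and month 3 comes before either possibility. The Provider line may also describe months 0 to 3 only. It does not say so, and it sits in a block whose Timing line concerns the 3-month visit, so clarification is still needed.
- *Note 2 directly contradicts the Provider line.* Note 2 speaks of patients. It reaches providers only by implication, because section 6.4 defines NTQ with a provider report. The explicit conflict is with section 6.2.
- *The intervention table settles the matter.* It shows no Arm 2 mark for the provider report, but none for the patient report either, which the usual-care text delivers at month 3. Its Arm 2 timing cell may also be cut off. It is weak evidence either way.

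**Conclusion.** The point holds. As written, section 9 does not estimate the contrast in the Aim 1 hypothesis, because the whole usual-care arm (30 of 60) is scheduled to have had the patient nudge and coaching for about 3 months by the 6-month visit. The consequence is a mislabelled planning estimate. No error rate is affected, and no size or direction of distortion is claimed; the differences in points above rest wholly on assumed rates.

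The conclusion assumes that delivery follows the schedule and that the delayed delivery comes after the 3-month assessment, as section 6.2 states for the provider and note 2 implies for the patient. It also takes the Timing line to govern the nudge and coaching in the usual-care Delivery lines. A reader might infer from those lines that usual care is nudged at baseline, but the Timing line places the report at the 3-month visit.

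The conflict between section 6.2 and the usual-care Provider line is real as written, but secondary. It decides only which delayed package the 6-month comparison concerns.

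**What to change.** In section 9:

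- Make the between-arm difference in treatment receipt from baseline to the 3-month assessment, before the delayed delivery, the Aim 1 estimate of NTQ versus usual care for R01 planning.
- Report the 6-month difference as a secondary comparison of immediate with delayed delivery.
- Replace the unclear time reference in the Aim 1 analysis with the period over which receipt is counted, and align note 1 of section 6.4 by naming the aim or aims it covers.

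Relabelling month 6 alone would not be enough, since it would leave the Aim 1 hypothesis without an analysis.

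Separately, the sponsor must reconcile section 6.2, the usual-care Provider, Content and Delivery lines in section 6.4, the intervention table and note 2, and state which passage governs. One schedule by component, arm and period (months 0 to 3 and 3 to 6) would do this, including whether the delayed delivery has a booster. Which components are delivered is for the sponsor to decide.

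The cost is a wording amendment and a shorter follow-up for the main Aim 1 estimate (3 months instead of 6). No patients, visits or assessments are added, because section 6.2 already assesses tobacco treatment at both times. The readable text does not give the recall period of those questions, so it should be checked against the period chosen.

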6.5 Remuneration

Patients will receive a \$50 gift card for each assessment completed (3 assessments = \$150).

6.6 Retrospective EHR query

De-identified EHR data will be queried, as approved by IRB. We will examine patient smoking prevalence, diagnosis codes, and proportion receiving tobacco treatment (medication and counseling) from EHR data. Data will be provided as approved by the Washington University Institutional review board.

7. Risks and Benefits

Participants may or may not benefit from being in this study. However, we hope that, in the future, other people might benefit from this study because knowledge generated from this research could advance the delivery of smoking cessation treatment.

Participation in this study does not entail any risks that are greater than those ordinarily encountered in daily life. It is possible that a participant will feel uncomfortable during the assessment. If that is the case, they can refuse to answer that particular question or discontinue the assessment altogether.

There is a risk of breach of confidentiality. All reasonable steps will be taken to ensure that patient privacy is maintained.

8. Regulatory and reporting requirements

We expect that the occurrence of a serious adverse event as it relates to these study interventions to be extremely rare. If a breach of confidentiality were to occur, it would be reported to QASMC and HRPO within 10 days of notification.

This study does not require QASMC audit or submission of DSM reports. In case of severe adverse events requiring immediate attention the study team will have a call schedule to ensure an on-call clinician and a back-up clinician are always available for the study team for safety assessment. If both the on-call clinician and back up clinician cannot be reached, the staff will recommend the participant to contact their existing primary care doctor or psychiatrist or go to the emergency room for evaluation and refer the participant to crisis hotline or other community resources that may be beneficial to the participant.

9. Statistical Considerations

Aim 1: test the effect of nudges to quit on patient receipt of tobacco treatment.

The investigators hypothesize patient receipt of tobacco cessation treatment such as medication and counseling will be higher after delivery of nudges to quit over usual care.

Aim 1 analysis: We will compare the patient receipt of tobacco treatment for smoking cessation during at 6 months visit across the 2 arms. This pilot trial will be limited in statistical power due to its small sample size, but will provide important estimates for R01 proposal power calculations.

Aim 2, the investigators will test the effect of nudges to quit on smoking behaviors.

The investigators hypothesize that smoking behaviors will decrease and quitting behaviors will increase in the nudges to quit group compared to usual care. This pilot trial will be limited in statistical power due to its small sample size, but will provide important estimates for R01 proposal power calculations.

Aim 3, the investigators will evaluate the feasibility and preliminary effect of this pilot project for a future R01 proposal to systematically evaluate this multilevel intervention adapted for CMHCs. These data will inform the design of a future larger well powered trial to evaluate the multilevel intervention rigorously. Participant perspectives on acceptability of the intervention, collected during follow up visits, will be used to motivate this future work.

This is a pilot trial to evaluate feasibility and preliminary effects. No statistical tests will be pursued.

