6.1 Study overview

The overarching goal of this pilot project is to reduce the disparity in the treatment of tobacco use among patients at psychiatry clinics with low burden, multi-level implementation strategies, a important need reflected in existing evidence and a recent survey of community needs. The investigators propose a pilot randomized trial of 60 patients. Patients will be randomized with 1:1 allocation to usual care vs. intervention “Nudges to Quit”.

TRIAL OVERVIEW	Recruit, Screen, Consent	Baseline	Follow Up	Follow Up
Timeline	Prior to baseline	Day 0	Month 3	Month 6
Location	Phone	Zoom/ Phone/ Study Lab	Zoom/ Phone/ Study Lab	Zoom/ Phone/ Study Lab
Remuneration	-	\$50	\$50	\$50
COMMUNICATIONS				

Mail Recruitment Letters/ Call to recruit/ Flyers	X			
ADMINISTRATIVE				
Screening/ Eligibility Check	X	X		
Informed Consent	X	X		
Contact Information		X		
ASSESSMENTS AND DATA				
Demographics		X		
Smoking History/Status		X	X	X
Smoking Treatment History and Interest		X	X	X
Bioverified point prevalence abstinence (patients reporting abstinence)			X	
Use of Nicotine and Tobacco		X	X	X
FTND		X	X	X
WSWS		X	X	X
Credibility, Acceptability and Expectancy		X	X	X
Readiness to Quit		X	X	X

FTND= Fagerström Test for Nicotine Dependence, WSWS= Wisconsin Smoking Withdrawal Scale; NTQ - Nudges to Quit; UC- usual care

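### Does Aim 1 need a written rule on whether the study team's own 5A's coaching counts as counseling received, and over what look-back?

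*Combined protocol and SAP*

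**What the plan says.** Section 2 and section 9 give the Aim 1 hypothesis in the same terms: "patient receipt of tobacco cessation treatment such as medication and counseling will be higher after delivery of nudges to quit over usual care". Section 9 then places the comparison of the two arms at the 6-month visit. It adds that the pilot has little power, that its estimates will inform the power calculation of a later R01 application, and that no statistical tests will be done.

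Section 6.4 describes verbal delivery of the nudge: "A study team member will deliver the patient nudge with a brief coaching interaction based on the public health service guidelines and 5A's approach". For Nudges to Quit (NTQ) this falls within 7 days of baseline, and the 1-month booster is sent by mail or email only. For usual care (UC) the same contact is tied to the 3-month visit, in line with the note under the intervention table: "After 3 months, patients in Arm 2 (UC) will receive NTQ intervention". That table also lets UC patients have the handout explained by staff: "Patient Basic Handout (mail, email and verbal delivery by a research team member if applicable"). The notes add a secondary look at UC over time, since "patients assigned to the UC arm may have increased treatment as they transition from UC to NTQ intervention".

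On data, the section 6.1 schedule lists "Smoking Treatment History and Interest" at baseline, month 3 and month 6, and section 6.2 says the study team assesses tobacco treatment at the follow-ups. Section 6.6 separately describes a de-identified query of the "proportion receiving tobacco treatment (medication and counseling) from EHR data". The only look-back for treatment is the 30-day one in the exclusion criterion of section 3.1.

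**The concern.** The 5A's is a tobacco-treatment framework. A participant asked about counseling since baseline could reasonably mention the study team's own coaching, the more so because research staff also administer the follow-up questionnaire. No sentence in the plan excludes that contact from the outcome, and no recall period is stated.

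The direction of any error would depend on the unstated window. A since-baseline count at 3 months would favour NTQ, because only NTQ is scheduled for nudge coaching by then. A since-baseline count at 6 months would dilute a true difference, because both arms have been coached. A count since month 3 would go against NTQ, and the secondary look within UC could show a rise made up of the coaching itself.

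The estimate is the product of this pilot. If it mixed delivery of the intervention with treatment obtained from a clinic, provider or quitline, a later trial could be wrongly sized. If the source of counseling were not recorded at the visit, the two might not be separable afterwards.

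**Working it through.** The plan gives no rate, effect size or power to reproduce, so the check has two parts.

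**What the text supports**

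- Section 9 speaks of receipt after the nudge is delivered. Section 6.4 lists coaching as a method of delivering the nudge. Read together, the coaching is the intervention and the outcome is what follows it.
- Section 3.1 uses counseling for cessation treatment, whereas section 6.4 calls the staff contact coaching.
- The provider nudge in section 6.4 concerns medication, cessation programs, advice and referral, all of them treatment from outside the study team.
- Sections 6.1 and 6.2 make the study assessments the evident source. The query in section 6.6 is retrospective and de-identified, and no link to the arms is described, so it is a weak rival.

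**How large an error could be**

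From section 6.1: 60 patients, 1:1, so 30 per arm. Assumed: outside receipt p from 0.10 to 0.30, equal in both arms unless stated; f1 and f0, the fractions of NTQ and UC patients whose staff contact is counted, independent of outside receipt.

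Measured receipt = 1 − (1 − p)(1 − f).

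1. *3 months, since baseline.* False difference = (1 − p)(f1 − f0).
   - f1 = 0.10, f0 = 0: 0.90 × 0.10 = 0.090 down to 0.70 × 0.10 = 0.070, or 7 to 9 points.
   - f1 = 0.25, f0 = 0: 0.225 down to 0.175.
   - f1 = 0.25, f0 = 0.10: 0.135 down to 0.105.
   - f1 = f0: zero.
2. *6 months, since baseline, equal f.* There is no false difference, but a true difference D reads as D(1 − f). For D = 0.15: 0.15 × 0.90 = 0.135, or 0.15 × 0.75 = 0.1125.
3. *6 months, since month 3.* Only UC is coached in the window, so the false difference is −f(1 − p): 7 to 9 points against NTQ at f = 0.10, and 17.5 to 22.5 at f = 0.25. The false rise within UC is the same size if f0 = 0 at month 3.
4. *30-day window.* Coaching near baseline or near month 3 lies outside the window at the next follow-up, so the error is about zero.

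**Against sampling error**

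With assumed receipt of 15% versus 30%, the standard error is sqrt(0.15 × 0.85/30 + 0.30 × 0.70/30) = 0.106, and the 95% half-width is 1.96 × 0.106 = 0.208.

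**Effect on sizing a later trial**

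Per arm, two-sided 5%, 80% power: n = 7.849 × (p1q1 + p2q2)/d².

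- 0.15 versus 0.30: 7.849 × 0.3375/0.0225 = 117.7, so 118.
- 0.15 versus 0.37 (0.30 inflated at 3 months by f1 = 0.10, f0 = 0): 7.849 × 0.3606/0.0484 = 58.5, so 59.
- True power for 0.15 versus 0.30 at 59 per arm: sqrt(0.3375/59) = 0.0756; 0.15/0.0756 − 1.96 = 0.02; power about 0.51.
- One standard error of sampling noise, UC held at 0.15: d = 0.256 gives about 44 per arm, and d = 0.044 gives about 1,150.

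**The case for a change.** The strongest opposing case is that the definition belongs in section 9, which is present in full, and is not there. Even if the questionnaire records who gave the counseling, section 9 does not say how the answers form the outcome. The error would be systematic, so a confidence interval does not cover it, and planning no tests does not help when the estimate is itself the product. With heavier miscounting it could be large: if 50% to 100% of an arm were coached and every contact counted, the false 3-month difference would run from 0.70 × 0.50 = 35 points to 0.90 × 1.00 = 90 points. The remedy would be cheap.

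Part of this stands. No sentence excludes the coaching, no outcome look-back is stated, and at a counted fraction of 0.25 the 3-month error (17.5 to 22.5 points) is about as large as the half-width.

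Three things limit it. Nothing in the documents supports counting every coached contact, and the intervention table qualifies verbal delivery with an if-applicable in both arms, so coaching may not reach all NTQ patients. The 118-versus-59 contrast uses the 3-month, since-baseline, f0 = 0 case, whereas section 9 places Aim 1 at 6 months, where the same 10% costs 15 − 13.5 = 1.5 points on a since-baseline count. And the harm needs a questionnaire that fails to separate study coaching from other counseling, which the documents do not show.

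**Conclusion.** This is missing detail that analysts would fill sensibly, not a rule that gives a wrong answer. The natural reading counts medication and counseling obtained after the nudge and treats the coaching as part of delivery. On that reading the error is zero at both visits and under any look-back. If the reading failed for 10% of coached patients, the 6-month difference would shrink by 1.5 points on a since-baseline count, and a 30-day count would be essentially unaffected. The less favourable cases, 7 to 9 points toward NTQ at 3 months or against it on a since-month-3 count, are below the 20.8-point half-width. Sampling noise alone moves the size of a later trial far more than the shift from 118 to 59 per arm.

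This rests on assumed rates (outside receipt 10% to 30%, 15% versus 30% for the benchmark), on counting being independent of outside receipt, and on questionnaire items that we cannot see. No change to the plan follows from this point.

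A separate matter is not settled here. The notes under the intervention table say "Outcomes will be assessed at 3 months post-intervention", while section 9 compares the arms at 6 months, after UC has received the intervention. That conflict exists however coaching is counted and should be judged on its own.

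### The only stated Aim 1 comparison is at month 6, three months after the usual-care arm is due the intervention, so it estimates immediate versus delayed nudges, not nudges versus usual care

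*Combined protocol and SAP*

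**What the plan says.** Sections 2 and 9 state the Aim 1 hypothesis as higher receipt of cessation treatment with nudges than with usual care. The analysis in section 9 is a single sentence: "We will compare the patient receipt of tobacco treatment for smoking cessation during at 6 months visit across the 2 arms". Section 9 adds that the pilot has limited power, that its estimates will feed the R01 power calculations, and that no statistical tests will be done.

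Section 6.4 describes the timing differently:

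- On the outcome time point, the notes under the intervention table say: "Outcomes will be assessed at 3 months post-intervention".
- On the control arm: "After 3 months, patients in Arm 2 (UC) will receive NTQ intervention". The usual-care timing entry reads: "We will deliver the intervention report on the day of or <=7 days of 3 month visit".
- The notes class the comparisons that this switch allows as secondary, and give as an example that "patients assigned to the UC arm may have increased treatment as they transition from UC to NTQ intervention".

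On the data, section 6.2 says: "At three month and three six months, the study team will assess tobacco treatment and smoking behaviors". The schedule in section 6.1 agrees, with smoking treatment history collected at baseline, month 3 and month 6.

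The documents disagree on how much of NTQ the usual-care arm eventually gets. Section 6.2 says: "If patients are randomized to usual care, the provider will receive the nudge following three month assessment". The usual-care provider entry in section 6.4 says, with no time limit: "Providers will maintain their usual care without receiving any reports".

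**The concern.** A between-arm difference estimates the effect of NTQ against usual care only while one arm is still on usual care. By the month 6 visit the usual-care patients have been due NTQ for about three months. The section 9 comparison is then NTQ from baseline, with a one-month booster, against NTQ from about month 3. Section 6.4 itself anticipates more treatment in the usual-care arm after the switch, which would narrow the difference.

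The wording of section 9 also leaves the outcome window open. Receipt could be cumulative from baseline to month 6 or could cover months 3 to 6 only. Both windows include the period after the switch, but the second loses more of the contrast.

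The absence of tests means that type I error is not at issue. The estimate is what the pilot is meant to deliver, and its stated use is to size the next trial. A trial planned from the month 6 difference would be sized for a contrast other than the one hypothesised.

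**Working it through.** The plan states no sample-size or power figure, so there is none to reproduce. The claim itself rests on the text; the arithmetic only shows how large the effect could be.

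**From the documents.** 60 patients allocated 1:1 give 30 per arm. Aim 1 is analysed at month 6, and the usual-care arm receives NTQ at month 3.

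**Assumed, because the documents give no rates.** Receipt per three-month interval is p0 under usual care and p1 under NTQ. Intervals are independent and the NTQ effect persists. After the switch, the usual-care arm's rate q is p0 (no switch), p0 + 0.5(p1 − p0) (half strength, for example the patient component alone) or p1 (full strength).

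**Cumulative receipt to month 6.** NTQ arm: 1 − (1 − p1)². Usual-care arm: 1 − (1 − p0)(1 − q).

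For p0 = 0.15 and p1 = 0.35, the NTQ arm is 1 − 0.65² = 0.5775.

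| Delayed delivery | Usual-care arm | Difference, months 0–6 | Difference, months 3–6 only (p1 − q) |
|---|---|---|---|
| None | 1 − 0.85 × 0.85 = 0.2775 | 0.300 | 0.20 |
| Half strength | 1 − 0.85 × 0.75 = 0.3625 | 0.215 | 0.10 |
| Full strength | 1 − 0.85 × 0.65 = 0.4475 | 0.130 | 0 |

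For p0 = 0.10 and p1 = 0.25, the NTQ arm is 1 − 0.75² = 0.4375. The usual-care arm is 0.19, 0.2575 or 0.325. The cumulative differences are 0.2475, 0.18 and 0.1125, and the months 3–6 differences are 0.15, 0.075 and 0.

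**Size of a later trial** (80% power, two-sided 5%), taking 15% and 35%:

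n per arm = (1.960 + 0.842)² × [pa(1 − pa) + pb(1 − pb)] / (pa − pb)², where (1.960 + 0.842)² = 7.851.

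- Month 6 cumulative, no switch (0.5775 vs 0.2775): 7.851 × 0.4445 / 0.0900 = 38.8, so 39.
- Month 6 cumulative, half strength (0.5775 vs 0.3625): 7.851 × 0.4751 / 0.0462 = 80.7, so 81.
- Month 6 cumulative, full strength (0.5775 vs 0.4475): 7.851 × 0.4912 / 0.0169 = 228.2, so 229.
- Months 3–6 only, half strength (0.35 vs 0.25): 7.851 × 0.4150 / 0.0100 = 325.8, so 326. At full strength the difference is zero and no size exists.
- Month 3 (0.35 vs 0.15): 7.851 × 0.3550 / 0.0400 = 69.7, so 70.

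**A simpler model as a cross-check.** Assume 20% versus 40% at month 3, and let the usual-care arm gain a share f of the NTQ effect by month 6. The 20-point difference becomes 15, 10, 5 or 0 points for f = 0.25, 0.5, 0.75 or 1. The size per arm rises from 82 undiluted to 152, 356 and 1,471 for the first three.

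**Precision of the month 3 estimate in this pilot.** 1.96 × √(0.35 × 0.65/30 + 0.15 × 0.85/30) = 0.213, or about ±21 points.

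**The case against.** The strongest reply is that this is a drafting conflict rather than a chosen analysis. Section 6.4 already points to month 3 for outcomes and treats comparisons after the switch as secondary, and the month 6 sentence in section 9 is visibly garbled. The uncontaminated data will be collected whatever section 9 says, and nothing obliges the investigators to ignore them when planning the R01. That is fair as to the likely intent, and it explains why the repair is cheap. It does not correct section 9: no section names a month 3 between-arm analysis for Aim 1, and an analyst following the plan would report month 6.

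The size of the effect is also open to challenge, and part of that stands. The 229 per arm is the extreme of the cumulative model. Half-strength delivery gives 81, not far from the 70 that month 3 rates give; for 10% versus 25% the corresponding figures are 106 and 97. Full strength is the least documented case, because no booster is stated for the usual-care arm and sections 6.2 and 6.4 disagree on the provider report. Similar totals do not make the contrasts equal, however. The 81 pairs a longer window with a diluted difference, whereas the same cumulative window without the switch needs 39.

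Finally, with 30 per arm neither estimate is precise: about ±21 points at month 3, and about ±25 at month 6 in the half-strength case. That also stands. Imprecision is expected in a pilot and can be shown with an interval; a mismatch between estimate and hypothesis cannot.

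**Conclusion.** The concern holds and should be corrected before analysis. As written, the sole Aim 1 comparison does not estimate the hypothesised effect of NTQ against usual care. This follows from the text alone, because the patient-level switch at month 3 is explicit whichever statement about providers applies.

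The amount of dilution is not known. It depends on whether delayed delivery works, on how much of NTQ the usual-care arm receives, and on the outcome window. Under the assumed rates, between about a quarter and all of the difference is lost: 30 points to 21.5 at the mild end (half strength, cumulative), 20 points to 0 at the severe end (full strength, months 3 to 6). If delayed NTQ had no effect there would be no dilution, but section 6.4 expects one. Moving to month 3 removes the dilution; it does not make a 60-patient estimate precise.

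**What to change.** In section 9, define the Aim 1 comparison as receipt of tobacco treatment from baseline to the month 3 visit, with that assessment completed before any nudge is delivered to the usual-care arm. Report the between-arm difference with its confidence interval, which needs no test. Describe month 6 as a secondary, descriptive comparison of immediate with delayed NTQ, and report receipt separately for months 0–3 and 3–6 so that the window is unambiguous.

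Reconcile sections 6.2 and 6.4 on whether usual-care providers receive the report after month 3, since this determines what the delayed arm received. Section 9 gives no time point for Aim 2; stating month 3 there as well would keep the aims consistent, though this is a suggestion and not a separate error.

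The cost is a wording change in section 9 and the reconciliation of sections 6.2 and 6.4. Tobacco treatment is already assessed at month 3 in both arms, so no patients, visits or data items are added.
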